10.2 Disease Parameters

To assess objective response or future progression, it is necessary to estimate the overall tumor burden at baseline and use this as a comparator for subsequent measurements. Measurable disease is defined by the presence of at least one measurable lesion.

10.2.1 *Measurable disease*

Measurable lesions are defined as those that can be accurately measured in at least one dimension (longest diameter to be recorded) as >20 mm by chest x-ray or as >10 mm with CT scan, MRI, or calipers by clinical exam. All tumor measurements must be recorded in millimeters (or decimal fractions of centimeters).

Note: Tumor lesions that are situated in a previously irradiated area are not considered measurable unless there has been demonstrated progression in the lesion.

10.2.2 *Malignant lymph nodes*

To be considered pathologically enlarged and measurable, a lymph node must be >15 mm in short axis when assessed by CT scan (CT scan slice thickness recommended to be no greater than 5 mm). At baseline and in follow-up, only the short axis will be measured and followed.

10.2.3 *Non-measurable disease*

All other lesions (or sites of disease), including small lesions (longest diameter <10 mm or pathological lymph nodes with ≥ 10 to <15 mm short axis), are considered non-measurable disease. Bone lesions, leptomeningeal disease, ascites, pleural/pericardial effusions, lymphangitic involvement of the skin or lung, inflammatory breast disease, and abdominal masses/abdominal organomegaly (not followed by CT or MRI), are considered as non-measurable.

Note: Cystic lesions that meet the criteria for radiographically defined simple cysts should not be considered as malignant lesions (neither measurable nor non-measurable) since they are, by definition, simple cysts.

‘Cystic lesions’ thought to represent cystic metastases can be considered as measurable lesions, if they meet the definition of measurability described above. However, if non-cystic lesions are present in the same patient, these are preferred for selection as target lesions.

10.2.4 *Target lesions*

All measurable lesions up to a maximum of 2 lesions per organ and 5 lesions in total, representative of all involved organs, should be identified as target lesions and recorded and measured at baseline. Target lesions should be selected on the basis of their size (lesions with the longest diameter), be representative of all involved organs, but in addition should be those that lend themselves to reproducible repeated measurements. It may be the case that, on occasion, the largest lesion does not lend itself to reproducible measurement in which circumstance the next largest lesion which can be measured reproducibly should be selected. A sum of the diameters (longest for non-nodal lesions, short axis for nodal lesions) for all target lesions will be calculated and reported as the baseline sum diameters. If lymph nodes are to be included in the sum, then only the short axis is added into the sum. The baseline sum diameters will be used as reference to further characterize any objective tumor regression in the measurable dimension of the disease.

10.2.5 *Non-target lesions*

All other lesions (or sites of disease) including any measurable lesions over and above the 5 target lesions should be identified as non-target lesions and should also be recorded at baseline. Measurements of these lesions are not required, but the presence, absence, or in rare cases unequivocal progression of each should be noted throughout follow-up.

10.3 Methods for Evaluation of Measurable Disease

All measurements should be taken and recorded in metric notation using a ruler or calipers. All baseline evaluations should be performed as closely as possible to the beginning of treatment and never more than 4 weeks before the beginning of the treatment.

The same method of assessment and the same technique should be used to characterize each identified and reported lesion at baseline and during follow-up. Imaging-based evaluation is preferred to evaluation by clinical examination unless the lesion(s) being followed cannot be imaged but are assessable by clinical exam.

10.3.1 *Clinical lesions*

Clinical lesions will only be considered measurable when they are superficial (e.g., skin nodules and palpable lymph nodes) and ≥ 10 mm diameter as assessed using calipers (e.g., skin nodules). In the case of skin lesions, documentation by color photography, including a ruler to estimate the size of the lesion, is recommended.

10.3.2 *Chest x-ray*

Lesions on chest x-ray are acceptable as measurable lesions when they are clearly defined and surrounded by aerated lung. However, CT is preferable.

10.3.3 *Conventional CT and MRI*

This guideline has defined measurability of lesions on CT scan based on the assumption that CT slice thickness is 5 mm or less. If CT scans have slice thickness greater than 5 mm, the minimum size for a measurable lesion should be twice the slice thickness. MRI is also acceptable in certain situations (e.g. for body scans).

Use of MRI remains a complex issue. MRI has excellent contrast, spatial, and temporal resolution; however, there are many image acquisition variables involved in MRI, which greatly impact image quality, lesion conspicuity, and measurement. Furthermore, the availability of MRI is variable globally. As with CT, if an MRI is performed, the technical specifications of the scanning sequences used should be optimized for the evaluation of the type and site of disease. Furthermore, as with CT, the modality used at follow-up should be the same as was used at baseline and the lesions should be measured/assessed on the same pulse sequence. It is beyond the scope of the RECISTv1.1 guidelines to prescribe specific MRI pulse sequence parameters for all scanners, body parts, and diseases. Ideally, the same type of scanner should be used and the image acquisition protocol should be followed as closely as possible to prior scans. Body scans should be performed with breath-hold scanning techniques, if possible.

10.3.4 *PET-CT*

At present, the low dose or attenuation correction CT portion of a combined PET-CT is not always of optimal diagnostic CT quality for use with RECIST v1.1 measurements. However, if the site can document that the CT performed as part of a PET-CT is of identical diagnostic quality to a diagnostic CT (with IV and oral contrast), then the CT portion of the PET-CT can be used for RECIST v1.1 measurements and can be used interchangeably with conventional CT in accurately measuring cancer lesions over time. Note, however, that the PET portion of the CT

introduces additional data which may bias an investigator if it is not routinely or serially performed.

10.3.5 *Ultrasound*

Ultrasound is not useful in assessment of lesion size and should not be used as a method of measurement. Ultrasound examinations cannot be reproduced in their entirety for independent review at a later date and, because they are operator dependent, it cannot be guaranteed that the same technique and measurements will be taken from one assessment to the next. If new lesions are identified by ultrasound in the course of the study, confirmation by CT or MRI is advised. If there is concern about radiation exposure at CT, MRI may be used instead of CT in selected instances.

10.3.6 *Endoscopy, Laparoscopy*

The utilization of these techniques for objective tumor evaluation is not advised. However, such techniques may be useful to confirm complete pathological response when biopsies are obtained or to determine relapse in trials where recurrence following complete response (CR) or surgical resection is an endpoint.

10.3.7 *Tumor markers*

Tumor markers alone cannot be used to assess response. If markers are initially above the upper normal limit, they must normalize for a patient to be considered in complete clinical response. Specific guidelines for both CA-125 response (in recurrent ovarian cancer) and PSA response (in recurrent prostate cancer) have been published [JNCI 96:487-488, 2004; J Clin Oncol 17, 3461-3467, 1999; J Clin Oncol 26:1148-1159, 2008]. In addition, the Gynecologic Cancer Intergroup has developed CA-125 progression criteria which are to be integrated with objective tumor assessment for use in first-line trials in ovarian cancer [JNCI 92:1534-1535, 2000].

10.3.8 *Cytology, Histology*

These techniques can be used to differentiate between partial responses (PR) and complete responses (CR) in rare cases (e.g., residual lesions in tumor types, such as germ cell tumors, where known residual benign tumors can remain).

The cytological confirmation of the neoplastic origin of any effusion that appears or worsens during treatment when the measurable tumor has met criteria for response or stable disease is mandatory to differentiate between response or stable disease (an effusion may be a side effect of the treatment) and progressive disease.

10.3.9 FDG-PET

While FDG-PET response assessments related to NSCLC management and to immunotherapy need additional study, it is sometimes reasonable to incorporate the use of FDG-PET scanning to complement CT scanning in assessment of tumor progression (particularly possible 'new' disease) or regression (evaluation of potential CR). Lesions can be assessed on FDG-PET imaging according to the following algorithm:

Negative FDG-PET at baseline, with a positive FDG-PET at follow-up is a sign of PD based on a new lesion.

No FDG-PET at baseline and a positive FDG-PET at follow-up: If the positive FDG-PET at follow-up corresponds to a new site of disease confirmed by CT, this is PD. If the positive FDG-PET at follow-up is not confirmed as a new site of disease on CT, additional follow-up CT scans are needed to determine if there is truly progression occurring at that site (if so, the date of PD will be the date of the initial abnormal FDG-PET scan). If the positive FDG-PET at follow-up corresponds to a pre-existing site of disease on CT that is not progressing on the basis of the anatomic images, this is not PD.

FDG-PET may be used to upgrade a response to a CR in a manner similar to a biopsy in cases where a residual radiographic abnormality is thought to represent fibrosis or scarring. However, it must be acknowledged that both approaches may lead to false positive CR due to limitations of FDG-PET and biopsy resolution/sensitivity.

Note: A 'positive' FDG-PET scan lesion means one which is FDG avid with an uptake greater than twice that of the surrounding tissue on the attenuation corrected image.

10.4 Response Criteria

10.4.1 Evaluation of Target Lesions

10.4.1.1 Complete Response (CR)

Disappearance of all target lesions. Any pathological lymph nodes (whether target or non-target) must have reduction in short axis to <10 mm.

10.4.1.2 Partial Response (PR)

At least a 30% decrease in the sum of the diameters of target lesions, taking as reference the baseline sum diameters.

10.4.1.3 Progressive Disease (PD):

At least a 20% increase in the sum of the diameters of target lesions, taking as reference the smallest sum on study (this includes the baseline sum if that is the smallest on study). In addition to the relative increase of 20%, the sum must also demonstrate an absolute increase of at least 5 mm. (Note: the appearance of one or more new lesions is also considered progressions).

10.4.1.4 Stable Disease (SD)

Neither sufficient shrinkage to qualify for PR nor sufficient increase to qualify for PD, taking as reference the smallest sum diameters while on study.

10.4.2 Special notes on the assessment of target lesions

10.4.2.1 Lymph nodes

Lymph nodes identified as target lesions should always have the actual short axis measurement recorded and should be measured in the same anatomical plane as the baseline examination, even if the nodes regress to below 10mm on study. This means that when lymph nodes are included as target lesions, the ‘sum’ of lesions may not be zero even if complete response criteria are met, since a normal lymph node is defined as having a short axis of < 10 mm.

10.4.2.2 Target lesions that become ‘too small to measure’

All lesions (nodal and non-nodal) recorded at baseline should have their actual measurements recorded at each subsequent evaluation, even when very small (eg, 2mm). If the radiologist is able to provide an actual measure, that should be recorded, even if it is below 5mm. When such a lesion becomes difficult to assign an exact measurement, it is recommended to: If it is in the opinion of the radiologist that the lesion has likely disappeared, the measurement should be recorded as 0 mm. If the lesion is believed to be present and is faintly seen but too small to measure, a default value of 5 mm should be assigned (note: in case of a lymph node believed to be present and faintly seen but too small to measure, a default value of 5 mm should be assigned in this circumstance as well). This default value is derived from the 5 mm CT slice thickness (but should not be changed with varying CT slice thickness).

10.4.2.3 Lesions that split or coalesce on treatment

When non-nodal lesions ‘fragment’, the longest diameters of the fragmented portions should be added together to calculate the target lesion sum. Similarly, as lesions coalesce, a plane between them may be maintained that would aid in obtaining maximal diameter measurements of each individual lesion. If the lesions have

coalesced such that they are no longer separable, the vector of the longest diameter in this instance should be the maximal longest diameter for the ‘coalesced lesion’.

10.4.3 Evaluation of Non-Target Lesions

10.4.3.1 Complete Response (CR):

Disappearance of all non-target lesions and normalization of tumor marker level. All lymph nodes must be non-pathological in size (<10 mm short axis).

Note: If tumor markers are initially above the upper normal limit, they must normalize for a patient to be considered in complete clinical response.

10.4.3.2 Non-CR/Non-PD:

Persistence of one or more non-target lesion(s) and/or maintenance of tumor marker level above the normal limits.

10.4.3.3 Progressive Disease (PD):

Appearance of one or more new lesions and/or unequivocal progression of existing non-target lesions. Unequivocal progression should not normally trump target lesion status. It must be representative of overall disease status change, not a single lesion increase.

Although a clear progression of “non-target” lesions only is exceptional, the opinion of the treating physician should prevail in such circumstances, and the progression status should be confirmed at a later time by the review panel (or Principal Investigator). When the patient also has measurable disease: To achieve ‘unequivocal progression’ on the basis of the non-target disease, there must be an overall level of substantial worsening in non-target disease such that, even in presence of SD or PR in target disease, the overall tumor burden has increased sufficiently to merit discontinuation of therapy. A modest ‘increase’ in size of one or more non-target lesions is usually not sufficient to qualify for unequivocal progression status. When the patients has only non-measurable disease: To achieve ‘unequivocal progression’ on the basis of the non-target disease, there must be an overall level of substantial worsening such that the overall tumor burden has increased sufficiently to merit discontinuation of therapy. A modest ‘increase’ in the size of one or more non-target lesions is usually not sufficient to qualify for unequivocal progression status. Because worsening in non-target disease cannot be easily quantified (by definition: if all lesions are non-measurable) a useful test that can be applied when assessing patients for unequivocal progression is to consider if the increase in overall disease burden based on the change in non-measurable disease

is comparable in magnitude to the increase that would be required to declare PD for measurable disease: i.e., an increase in tumor burden representing an additional 73% increase in ‘volume’ (which is equivalent to a 20% increase diameter in a measurable lesion). Examples include an increase in a pleural effusion from ‘trace’ to ‘large’, an increase in lymphangitic disease from localized to widespread, or may be described in protocols as ‘sufficient to require a change in therapy’. If ‘unequivocal progression’ is seen, the patient should be considered to have had overall PD at that point.

10.4.4 Evaluation of Best Overall Response

The best overall response is the best response recorded from the start of the treatment until disease progression/recurrence (taking as reference for progressive disease the smallest measurements recorded since the treatment started). The patient's best response assignment will depend on the achievement of both measurement and confirmation criteria.

Target Lesions	Non-Target Lesions	New Lesions	Overall Response	Best Overall Response when Confirmation is Required*
CR	CR	No	CR	≥ 4 wks. Confirmation**
CR	Non-CR/Non-PD	No	PR	≥ 4 wks. Confirmation**
CR	Not evaluated	No	PR	
PR	Non-CR/Non-PD/not evaluated	No	PR	
SD	Non-CR/Non-PD/not evaluated	No	SD	Documented at least once ≥ 4 wks. from baseline**
PD	Any	Yes or No	PD	no prior SD, PR or CR

Any	PD***	Yes or No	PD	
Any	Any	Yes	PD	

* See RECIST 1.1 manuscript for further details on what is evidence of a new lesion.

** Only for non-randomized trials with response as primary endpoint.

*** In exceptional circumstances, unequivocal progression in non-target lesions may be accepted as disease progression.

Note: Patients with a global deterioration of health status requiring discontinuation of treatment without objective evidence of disease progression at that time should be reported as “*symptomatic deterioration*.” Every effort should be made to document the objective progression even after discontinuation of treatment.

10.5 Duration of Response

10.5.1 Duration of overall response:

The duration of overall response is measured from the time measurement criteria are met for CR or PR (whichever is first recorded) until the first date that recurrent or progressive disease is objectively documented (taking as reference for progressive disease the smallest measurements recorded since the treatment started).

The duration of overall CR is measured from the time measurement criteria are first met for CR until the first date that progressive disease is objectively documented.

10.5.2 Duration of stable disease:

Stable disease is measured from the start of the treatment until the criteria for progression are met, taking as reference the smallest measurements recorded since the treatment started, including the baseline measurements.

10.6 Progression-Free Survival

PFS is defined as the duration of time from start of treatment to time of progression or death, whichever occurs first.

11. STATISTICAL CONSIDERATIONS

The primary outcome of this study is overall response rate (CR+PR via RECIST 1.1). We will use a Simon's optimal 2-stage design with 80% power and 5% one-sided type-I error to compare the null hypothesis of ORR=5% vs. the alternative of ORR=20%. The first stage will enroll 10 patients, and if 1 or more responses are observed an additional 19 patients will be enrolled. If at least 4 responses are observed out of the 29 patients, the null hypothesis will be rejected

Safety Monitoring: We will monitor adverse events (AEs) throughout the study. If it appears that the risk of a serious AE is excessive, we will evaluate the treatment regimen and either modify the treatment plan or consider stopping the study. The risk of a serious AE (or DLT as defined above) is excessive if the risk is greater than 25%. Our stopping criterion corresponds to our determining that there is 75% or greater probability that the risk of a DLT exceeds 25%. Experience with single-agent anti-PD1 therapy suggests that the risk of a serious AE is between 15% and 20% but may be higher with the combination. We characterize this estimate with uncertainty using a beta distribution with parameters 2 and 8. This distribution has mean 0.2 and 90% probability that the risk is between 4% and 43%. The following table shows the stopping boundaries for safety monitoring.

Number of patients experiencing a DLT	4	5	6	7	8	9	10	11
Number of patients treated	4 - 6	7 - 9	10 - 13	14 - 17	18 - 20	21 - 24	25 - 27	28 - 29

Estimates of the operating characteristics for this stopping rule, as estimated from 5,000 simulations for each scenario, are as follows.

Risk of DLT	0.10	0.15	0.20	0.25	0.30	0.35	0.40	0.45	0.50
Chance of declaring the combination too toxic	1.2	4.8	14.2	31.2	51.7	71.5	86.9	94.9	98.3
Average sample size	28.8	28.1	26.6	24.0	20.8	17.2	13.7	11.1	9.1

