11.2 Interim Analysis

The first stage will enroll 10 patients, and if 1 or more responses are observed an additional 19 patients will be enrolled. After the first 6 patients are accrued, the regimen will be evaluated for toxicity. If 2 or more patients experience a DLT, the study will be halted for excess toxicity.

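### Section 11 gives power and average sample size for each stopping rule on its own; neither describes the trial run with all its stopping rules together

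*Combined protocol and SAP*

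**What the plan says.** Section 11 sets the efficacy test as Simon's optimal "2-stage design with 80% power and 5% one-sided type-I error to compare the null hypothesis of ORR=5% vs. the alternative of ORR=20"%. Section 11.2 repeats the futility rule: "The first stage will enroll 10 patients, and if 1 or more responses are observed an additional 19 patients will be enrolled". The final rule in Section 11 is: "If at least 4 responses are observed out of the 29 patients, the null hypothesis will be rejected".

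Section 11 then adds safety monitoring on the same patients. The prior is given as "We characterize this estimate with uncertainty using a beta distribution with parameters 2 and 8", and the trigger as "Our stopping criterion corresponds to our determining that there is 75% or greater probability that the risk of a DLT exceeds 25"%. On a signal the team will "either modify the treatment plan or consider stopping the study". A table of stopping boundaries follows, then a second table introduced by "Estimates of the operating characteristics for this stopping rule, as estimated from 5,000 simulations for each scenario, are as follows". For DLT risks of 10, 15, 20, 25 and 30% it prints a chance of declaring the combination too toxic of 1.2, 4.8, 14.2, 31.2 and 51.7%, and an average sample size of 28.8, 28.1, 26.6, 24.0 and 20.8.

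Section 11.2 adds a further toxicity look after six patients, with a mandatory halt if two or more have had a DLT.

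No section gives power, type I error or expected enrolment for these rules acting together. None says that the 80% assumes no toxicity stop, or that the average sample sizes assume no futility stop.

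**The concern.** Three stopping rules act on one cohort of 29: the 0-of-10 futility stop, the Section 11 toxicity rule and the Section 11.2 six-patient halt. A reader of Section 11 would take 80% as the chance that an active regimen (ORR 20%) ends in a positive trial, and the average sample sizes as expected enrolment. Both can be well off if each was worked out with the other rules switched off.

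This matters because the toxicity stops can act often at risks the plan regards as acceptable. It calls a risk above 25% excessive, and says that single-agent experience "suggests that the risk of a serious AE is between 15% and 20% but may be higher with the combination". At such risks an active regimen can be lost to a toxicity stop, and the printed table understates how often that happens if the six-patient halt is applied.

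**Working it through.** **Inputs.** From Sections 11 and 11.2: n1 = 10, stop if 0 responses; n = 29, reject if ≥4 responses; ORR 5% and 20%; Beta(2,8) prior with stopping when Pr(DLT risk > 0.25 | data) ≥ 0.75; the printed boundaries; the halt for ≥2 DLTs in six. Assumptions not in the documents: response and DLT are independent, outcomes are known at once, the Section 11 toxicity rule is checked after every patient, and any crossing ends the trial without rejecting the null.

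**1. Reproduce the 80%.** P(reject) = Σ P(X1 = x)·P(X2 ≥ 4 − x) for x ≥ 1, with X1 ~ Bin(10, p) and X2 ~ Bin(19, p). At p = 0.20: 0.2684 × 0.7631 + 0.3020 × 0.9171 + 0.2013 × 0.9856 + 0.1209 = **0.8011**. At p = 0.05 the sum is 0.0468. No toxicity term enters, so the stated 80% is the Simon rule alone.

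**2. Reproduce the safety table.** Run the 75% posterior rule to 29 patients with no other stop (exact recursion):

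| DLT risk | 10% | 15% | 20% | 25% | 30% |
|---|---|---|---|---|---|
| Too toxic, printed (%) | 1.2 | 4.8 | 14.2 | 31.2 | 51.7 |
| Too toxic, recomputed (%) | 1.0 | 4.9 | 14.7 | 31.5 | 52.3 |
| Average N, printed | 28.8 | 28.1 | 26.6 | 24.0 | 20.8 |
| Average N, recomputed | 28.8 | 28.1 | 26.5 | 24.0 | 20.6 |

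The match is within simulation error. The table is therefore the 75% rule alone, with neither the futility stop nor the six-patient halt. The printed boundaries run alone give 0.3, 2.1, 8.0, 20.5 and 39.3% too toxic. At many patient counts they need one DLT more than the criterion (6 of 10 against 5 of 10, for example).

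**3. Ceiling on average N.** With the futility stop and no toxicity at all, E(N) = 10 + 19 × [1 − (1 − p)^10].
- ORR 20%: 10 + 19 × (1 − 0.1074) = **26.96**
- ORR 5%: 10 + 19 × (1 − 0.5987) = **17.62**

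The printed 28.8 and 28.1 lie above both. Toxicity stops lower the average further:

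| Average N with futility stop, by DLT risk | 10% | 15% | 20% | 25% | 30% |
|---|---|---|---|---|---|
| ORR 20%, 75% criterion | 26.8 | 26.1 | 24.7 | 22.4 | 19.4 |
| ORR 5%, 75% criterion | 17.5 | 17.2 | 16.5 | 15.3 | 13.7 |
| ORR 20%, printed boundary | 26.9 | 26.7 | 25.9 | 24.3 | 21.9 |

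The 10–20% columns of the printed table are too high under either boundary.

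**4. Six-patient halt.** P(≥2 of 6) = 1 − (1 − q)^6 − 6q(1 − q)^5.
- q = 0.15: 1 − 0.3771 − 0.3993 = 0.224
- q = 0.20: 1 − 0.2621 − 0.3932 = 0.345
- q = 0.25: 1 − 0.1780 − 0.3560 = 0.466

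The printed chances of declaring the combination too toxic at these risks are 4.8, 14.2 and 31.2%.

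**5. Power at ORR 20%.** Under independence, P(reject) = 0.8011 × P(no toxicity stop). For the 75% criterion at 15%, 20% and 25% risk: 0.8011 × (1 − 0.049) = 0.762; × (1 − 0.147) = 0.684; × (1 − 0.315) = 0.549. For the halt alone: 0.8011 × (1 − 0.224) = 0.622; × (1 − 0.345) = 0.525; × (1 − 0.466) = 0.428.

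| Toxicity rule added to Simon | 10% | 15% | 20% | 25% |
|---|---|---|---|---|
| 75% criterion | 79% | 76% | 68% | 55% |
| Printed boundary | 80% | 78% | 74% | 64% |
| Six-patient halt alone | 71% | 62% | 53% | 43% |
| Halt plus either Section 11 rule | 71% | 62% | 50–51% | 37–40% |

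**6. Type I error.** Under the 75% criterion it falls from 0.047 to 0.046, 0.045, 0.040 and 0.032 at DLT risk 10, 15, 20 and 25%.

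**The case against.** Neither figure is miscalculated. Section 11 attaches 80% to the Simon design and presents the table as belonging to the safety rule, and quoting Simon power without toxicity stops is common practice. For the rule the table describes, a reader can even multiply the two printed figures: 80% × (1 − 14.2%) = 69% at 20% DLT risk. The Section 11 toxicity rule is also discretionary. All of this stands. It makes the point one of labelling and completeness rather than arithmetic, and it makes the losses from that rule upper bounds. It does not cover the average sample sizes, which leave out a futility stop stated in the same section, or the Section 11.2 halt, which appears in neither figure and is not discretionary.

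Four stronger readings are tempting but unsupported:
- *A completed, non-positive trial had less than 80% power.* Under independence, power given no toxicity stop is still 80%. What falls is the unconditional chance of a positive result.
- *None of the printed average sample sizes can occur at an ORR up to 20%.* That is true at 10–20% DLT risk. At 25–45% under the printed boundary, the average N at ORR 20% lies above the printed value and at ORR 5% below it (24.3 and 16.3 against 24.0 at 25%), so some ORR in between gives it. At ORRs well above 20% the futility stop is rare and the printed values are nearly right.
- *The false-positive rate is affected.* Toxicity stops can only lower it.
- *The plan expects a 15–20% DLT risk for this combination.* That is its single-agent serious-AE figure, which it says may be exceeded.

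Nor do the documents say that anyone planned oversight or drug supply on the printed averages.

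**Conclusion.** The point holds as a reporting gap with practical size. The loss of unconditional power depends on which toxicity rule is in force. With the Section 11 rule alone it is small at 15% DLT risk (about 2 to 4 points) and 6 to 12 points at 20%, at most. The Section 11.2 halt does most of the damage: on its own it stops the trial 22% of the time at 15% risk and 34% at 20%, both below the plan's own 25% limit, and takes power to 62% and 53%. The sizes rest on independence and immediate outcomes, since the documents give no correlation or reporting delay. The ceilings of 26.96 and 17.6 need no assumption about DLTs.

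**What to change.** In Section 11, state now that the 80% power is conditional on no toxicity stop, and that the existing table describes the 75% criterion alone, run to 29 patients without the futility stop or the six-patient halt.

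The 75% criterion, the printed boundaries and the Section 11.2 halt do not agree and must be reconciled; which to keep is for the trial team. Once that is settled, replace the table with a joint one: ORR 5% and 20% by DLT risk, including the stage-1 futility stop and every toxicity stop retained. It should report P(reject H0), P(toxicity stop), P(futility stop) and average N, and state how a crossing of a discretionary boundary is counted.

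The cost is one short simulation and a less favourable stated power. The sample size and the efficacy decision rule do not change.
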